For the continuous study outcomes, changes from baseline to three months will be compared between the study arms using two-sample, two-sided t-tests with 5% type I error rates. Changes in QOL and number of steps will be compared between the two treatment sequences using two-sample two-sided t-tests. No adjustments will be made for multiple testing. Means, SDs, medians, ranges, and frequency distributions will be reported and plotted over time by study arm. Additional analyses will compare changes from baseline to three months. Linear models will be used to assess the impact of treatment arm on three month outcomes after adjusting for the corresponding baseline measure and other variables related to the outcome (age, degree of breathlessness at baseline using the mMRC, and FEV1). Repeated measures mixed models will be used to estimate the intervention effect over the three months of the comparison study. Although there is a crossover element to the study design, crossover analyses will not be used due to the anticipated carryover effect in the intervention arm. Intent-to-treat analyses will also be performed to determine the sensitivity of the results to dropouts and missing values. In the intent-to-treat analyses, if a month three measure is missing for any reason, it will be described as not changing from baseline. Health care utilization (number of ED visits, hospitalizations, and length of stay) between baseline and three months will be treated (analyzed) as both binary (for incidence rates) and continuous (for the number of events). The binary endpoints will all be compared between groups using Fisher's exact test. Logistic regression models will also be fit to look for differences in these outcomes by arm after adjusting for age, mMRC, FEV1, baseline levels of anxiety, depression, and fear, and baseline health care utilization (before starting the study). While significant missing-ness (>5%) in the Aim 1 outcome is not expected, imputation is planned in case it is.

Descriptive summaries of the changes between baseline, three, six, and nine months will be used to assess the effect of the delayed intervention on the control arm and the residual beneficial effect on the intervention arm. These results will be only descriptive and exploratory. No formal hypothesis testing will be done. All data will be stored in REDCap and analyzed using SAS (Cary, NC).

Missing Values treatment: Initially, Little's test for missing completely at random (MCAR)³⁶ will be used along with Potthoff and colleagues assessment of missing at random (MAR+).³⁷ Contingent on either MCAR or MAR data, imputation will be considered in order to respond to the level of missing-ness and to be able to use the optimal amount of information in our model. In case of participant withdrawal, all available data will be used.

Path analysis: The hypothesized framework will be tested using structural equation modeling (SEM), which allows us to examine multiple dependent variables in one model and concurrently describe multiple paths of direct and indirect effects among the theoretical constructs. We will use two steps in SEM analyses. First, the validity of the measures will be assessed by fitting a measurement model and investigating whether the items are strong indicators of the latent constructs (e.g., self-efficacy and quality of life). The second step involves testing the effect of the predictor variables (e.g., MI training, mastery in PA, social persuasion, physiological and emotional states) on the outcome variables (e.g., self-efficacy, self-management, and physical QOL) with a particular interest in the role self-efficacy has in increasing self-management and physical QOL. In addition to the direct effects of MI training on self-efficacy, self-efficacy on self-management, self-management on physical QOL, mediating effects can be tested, such as the effects of MI training on self-management and physical QOL, or effects of self-efficacy on physical QOL by estimating their indirect effects. The model will be tested using lavaan, the R software package for SEM.³⁸ The model fit will be examined by its model χ^2 , goodness-of-fit index (GFI), and root mean square error of approximation (RMSEA).

Qualitative Analysis (Aim 4): Perceptions of the participants and the interventionist will be captured using qualitative methods. Qualitative inquiry in randomized controlled trials help interpret results and variation in results.³⁹ It can also help ensure that interventions meet stakeholder needs and therefore aid in future transferability of interventions like the proposed system. This is increasingly important as trials move out of controlled settings and into the social context of natural settings,⁴⁰ including participant homes.

This qualitative approach is part of an embedded mixed-methods design, a design commonly used when individuals' perspectives inform experimental results.(33) This aim also helps us better understand the contextual factors related to implementation. As such, it

reflects the principles of a type 1 hybrid effectiveness-implementation design, the rationale for which is to study barriers and facilitators to widespread implementation alongside the intervention's effectiveness, speeding future translation into practice.⁴¹

The interview instruments will be informed by the quantitative study aims, and quantitative results will guide the qualitative sampling plan. Specifically, the purposive sampling for interviews and in order to increase the breath of representativeness of the interviewees, we will use baseline scores on the Patient Activation Measure to stratify the population available for interview recruitment, and we will aim to interview 10 patients with lower levels of activation at baseline (Stages 1 and 2 indicating lower participant engagement) and 10 patients with higher levels (stages 3 and 4 indicating higher engagement) AND patients with high severity defined by a MRC dyspnea score 3-4 (10 participants) vs. low severity -score 0-2-(10 participants). This variation in the sample will better ensure a range of experiences in the data and allow understanding of different opinions and outcomes. Patient activation in particular has been shown to impact adherence to self-care regimens, including home monitoring.

Data Collection

The primary method of qualitative data collection will be individual semi-structured interviews with a sample of participants in the intervention arm (n=40) and study interventionists (n=4). Interviews will be conducted at approximately week 12 (around the time of the last interventionist call). We will use an interview guide—reviewed by experts (patients and clinicians)—to ask a combination of broad, open-ended questions and focused questions eliciting information about: 1) the participant's impressions of the program; 2) impressions of program effectiveness or perceived benefits; and 3) participant's prior experience with coaching. The interview guide will be informed by program theory, (i.e., self-efficacy theory and MI)^{15, 16} and the underlying constructs of measures from Aims 1-3.

To understand the feasibility and acceptability of the program, participants will be asked if they would recommend the program to another patient with COPD and what, if anything, they would change. Questions will also elicit feedback on the use of technology and barriers and facilitators to long-term adoption. We will ask interventionists to assess perceptions of how well the program fits within the current clinical services delivery system and which methods should be modified to enhance feasibility, acceptability, and durability of the intervention. Interventionists will be interviewed twice during the study in order to assess program delivery, including whether the intervention is being delivered as expected, at different points in the study implementation. Interviews will be conducted by a qualitative research analyst not involved in the intervention. They will take place *by phone and be audio recorded* and transcribed verbatim. After each interview, the interviewer will take detailed notes that describe the context of the interview, emerging themes or issues that arose in the interview, areas for clarification, and other comments. These notes and transcripts will be used in analysis. Per the reviewers' suggestions, we purposefully included a qualitative expert, [name], to conduct this analysis and work collaboratively with [name], as they have previously reported qualitative analysis together.⁴²

Qualitative Analysis Plan

Qualitative methods will use directed content analysis. This approach is useful when existing theory informs research questions, and researchers are interested in extending the theory or using it to make predictions or look for relationships among variables.⁴³ At least two investigators will review the data and use an iterative process to develop labels or codes and then higher-order categories that represent key themes related to the study aims. These will be informed by the theoretical assumptions in Aims 1-3. A coding framework will be independently applied to transcripts before the investigators discuss and agree on coding. Data will be entered into NVivo software (NVivo 10.1, QSR International Pty. Ltd.) or another system for text data management to facilitate queries.

Integration with Aims 1-3: The function of the mixed-methods design is elaboration of the quantitative data on effectiveness with the qualitative findings. After initial quantitative and qualitative analyses are complete, the investigators will place findings side-by-side to explore connections as well as divergent findings that need further exploration. This includes within- and between-case analysis to understand the perspectives of participants who differed on comparative effectiveness outcomes (Aim 1-3) as well as those who differed in important baseline characteristics such as participant activation.

Sample Size: We will enroll a total of 200 participants, with 100 in each arm. Sample size calculations are based on two-sample, two-sized t-tests comparing the two groups at 3 months. **Aim 1:** We calculated the sample size based on estimates from our previously published data⁶. From this research, the CRQ has a SD of about 1.13. A total sample of 189 participants (94 or 95 per group) is needed to detect a difference of 0.5 (the minimal clinically important difference) in the CRQ with 80% power. Based on our previous health coaching application (R01HL09468 [name], PI),⁶ we expect 5% attrition. We will therefore enroll 200 participants, 100 in each arm.

Aim 2: A sample size of 128 is needed to detect a half SD change in SMAS-30 based on COPD studies using this measure. **Aim 3:** The number of steps recorded by the AM is considered a valid measure of PA in patients with COPD and the elderly. The clinically meaningful difference in steps is estimated at 1100. Therefore, a sample size of 170 participants (85 per group) is needed considering a SD of 2500 steps from our previous study.⁶ **Aim 4:** The sample size of 40 completed participant interviews is within standards for qualitative research, but interviewing and analysis will take place concurrently and iteratively to inform the sampling plan. We will continue interviewing until saturation (the point at which interviews are not yielding much new information) is reached; the sample

will be increased as needed to more fully understand variation in the data,⁴⁴ especially between those who have low (versus high) levels of initial participant activation or those who differ in comparative-effectiveness outcomes. We will ensure ample participants to represent a range of opinions and investigate variation, rather than statistical testing. In regard to interventionist data collection, we will invite all interventionists (n=4) in the study to complete an interview; based on our pilot data, we expect high participation.

Limitations: While comparing the proposed intervention to center-based PR would be the ideal study, it would not be feasible because most participants cannot attend PR weekly (about 70%)³ and the study would be unlikely to accrue sufficiently. This study is geared to capture the population willing to do home PR, and individuals who are confident using technology: results may not be generalizable to all individuals with COPD. We realize that some participants randomly assigned to the control group will receive center-based PR, and we plan to document and adjust our model analyses accordingly (intention-to-treat analysis) despite this limitations, the study will address a critical need in COPD care: bringing PR to all individuals with COPD.

Conclusions

The proposed study will be the first of its kind combining monitored home-based PM with theory-driven SM support through health coaching. Since there is no system available for home-based PR delivery the results of this application are critically needed in the field of COPD. We envision that the proposed intervention is feasible (already tested) and using commercially available software and hardware will be ready to be disseminated if effective. Health Coaching will bring higher participant engagement, better participant provider communication, and possibly improved outcomes. Inclusion of qualitative inquiry will strengthen our understanding of our results and provide further information for implementation/ dissemination

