In our previous work, we developed and tested (R01 HL09468), an effective program for SM in COPD through health coaching¹³ rooted in motivational interviewing (MI)^{13,14} that decreased COPD re-hospitalizations⁶ and produced a sustained improved QOL at six and 12 months.

Theoretical Framework

The theoretical framework of the proposed intervention (Fig. 1) is based on two guiding theories: self-efficacy theory^{15,17} and MI theory.¹⁶ In brief, training in MI prepares the health coach to initiate conversations in the spirit of MI (compassion, acceptance, evocation of the client's values, and collaboration) and skills (open questions, a non-coercive approach for change, and making the participant the expert and final decision-maker). The latter (spirit and skills) may not only impact social persuasion (part of self-efficacy theory) but also directly increase self-efficacy (confidence) that leads to higher SM abilities (behavior change). Pulmonary rehabilitation directly impacts the foundations of the self-efficacy theory: mastery in PA, by engaging in daily exercises (Aim 3, measured by activity monitor), social persuasion (weekly feedback from a trustworthy coach) and emotions and physiology (exercise is a known positive factor impacting emotions and COPD physiology). Self-efficacy (Sub aim 2 measured by CRQ Mastery) translates into SM or behavior change (Aim 2 measured by SMAS30) which in turn impacts physical QOL (Aim 1). We have recently confirmed and published the independent relationship between MI health coaching, SM and quality of life.^{6,18,19} A proposed path analysis will confirm the proposed framework.

*Compassion, Acceptance, Evocation, Collaboration; †Open-ended questions, affirmations, reflective listening, and summaries

Fig. 1. Theoretical framework.

Innovation

The project is truly innovative due to the purely home-based nature of the system, the simplicity and accuracy of data collection attained with using commercially available monitors, and the addition of health coaching to engage and provide weekly feedback to participants. Previous studies required participants in home-based training groups to attend SM education^{4,20} or weekly monitoring in the clinic or hospital.²¹ These approaches fail to overcome the transportation and mobility-related barriers to attendance, perpetuating the present lack of adherence.

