The interviews will be recorded for subsequent transcription of the interactions. The transcribed interviews will be examined for common themes. Each interview will vary between 20 and 30 minutes and will be performed by a member of the Mindful Breathing Laboratory who is trained in Motivational Interviewing and Qualitative Interviewing. Additional members from the Lab will assist in the transcription of the interviews as well as theme identification. Data collection and analysis will be overseen by [name]. (A guided interview script will be used.)

In addition, the five Mayo Clinic staff who served as health coaches on the study will also be offered the opportunity to be interviewed to learn their experiences in the program. The interviews will be conducted by Qualitative Expert, [name], either in a private space or by phone call. The interview will be recorded so that it can later be transcribed and analyzed. An email inviting the health coach to participate will be sent to the health coach. The health coach will be orally consented and will have the option to opt out.

[figure not shown]

Fig. 9. Randomized study design.

Questionnaires:

Physical QOL will be assessed by the CRQ (Aim 1), SM abilities, self-efficacy (Aim 2), and daily PA and self-efficacy for exercise (Aim 3). These QOL components will be measured at baseline, three, six, and nine months after randomization in both groups. Qualitative analysis (Aim 4) will occur after the intervention in order to further understand the intervention's acceptability and to help interpret the comparative effectiveness findings from Aims 1-3.

Additional QOL questionnaires will include the Interpersonal Support Evaluation List (ISEL-12), the Meaning of Life Questionnaire (MLQ6), and the Longitudinal Analogue Self-Assessment (LASA6). Recent research has indicated that social support and sense of meaning of life are important indicators in the perception of quality of life. The added questionnaires will better measure these important factors.

Study Sites:

The clinical study sites include (1) Mayo Clinic—Rochester, Rochester, MN, (2) Mayo Clinic-Jacksonville, Jacksonville, FL, and (3) HealthPartners® Specialty Center-Regions Hospital, St. Paul, MN. The engineer site is Minnesota HealthSolutions, Maple Grove, MN. These study partners have collaborated for the past five years.

Recruitment

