Data will be stored in Mayo Clinic's REDCap database. Mayo Clinic Florida and Health Partners will only be able to see data from their site. Mayo Clinic Rochester will have access to data entered into REDCap as they are the coordinating site for this trial. REDCap (Research Electronic Data Capture) is a secure, web-based application designed to support data capture for research studies, providing: 1) an intuitive interface for validated data entry; 2) audit trails for tracking data manipulation and export procedures; 3) automated export procedures for seamless data downloads to common statistical packages; and 4) procedures for importing data from external sources.

Health Coaches located at Mayo Clinic Rochester may fill in as Health Coaches at other sites to cover vacations, absences and employment gaps in health coaches. Mayo Clinic Rochester Health Coaches only have access to data in REDCap (demographics and health coach notes) and not the medical record.

Data Analysis and Data Safety Monitoring

DSMB

See Data Safety Monitoring Charter.

Analysis Plan

Page 11 of 17

There are three *distinct* quantitative study hypotheses (inform different aspects of the process). Hypothesis 1 (Aim 1) states that participants on home-based PR will have higher physical (dyspnea fatigue) QOL at month three than participants in the waitlist control group as measured by the CRQ physical summary score. Hypothesis 2 (Aim 2) is that participants on home-based PR will have better SM abilities at month three than participants in the waitlist control group. The SMAS-30 will be used to test this hypothesis. Hypothesis 3 (Aim 3) is that participants on home-based PR will have more daily PA than participants in the control group at month three. This will be measured by steps and minutes spent in sedentary, light, and moderate activity measured by the ActiGraph^{34,35} and greater self-efficacy for exercise. This study has two activity monitors, the ActiGraph, a gold standard activity monitor used for outcome measures (7-day wearing) at baseline, 3, 6 and 9 months. The Garmin Vivofit PR activity monitor used daily during PR period will NOT be used as an outcome measure, just for health coaching and participant awareness of physical activity (participant will keep this activity monitor after PR).

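### The path analysis is said to confirm that self-efficacy drives self-management and then physical QOL, but with same-visit measures and no reversed model it can show only consistency with that order

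*Combined protocol and SAP*

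**What the plan says.** **Theoretical Framework.** The order is explicit: "Self-efficacy (Sub aim 2 measured by CRQ Mastery) translates into SM or behavior change (Aim 2 measured by SMAS30) which in turn impacts physical QOL". The same paragraph ends its argument with "A proposed path analysis will confirm the proposed framework".

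**Study Design and Methods, Questionnaires.** Physical QOL, self-management abilities and self-efficacy are listed together, and "These QOL components will be measured at baseline, three, six, and nine months after randomization in both groups".

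**Analysis Plan, Hypothesis 1.** The QOL outcome is taken "as measured by the CRQ physical summary score". It therefore comes from the same questionnaire as CRQ Mastery, the self-efficacy measure.

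**Analysis Plan, Path analysis.** Two sentences describe the structural model, and they do not clearly describe the same one.

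- The first tests predictor variables, MI training among them, "on the outcome variables (e.g., self-efficacy, self-management, and physical QOL) with a particular interest in the role self-efficacy has" in raising the other two.
- The second lists "direct effects of MI training on self-efficacy, self-efficacy on self-management, self-management on physical QOL", and treats the remaining effects as mediated.

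Fit is judged by the model chi-square, "goodness-of-fit index (GFI), and root mean square error of approximation (RMSEA"). The paragraph does not say which visit supplies each variable. It mentions no lag, baseline adjustment, or competing or reversed model.

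**Analysis Plan, general.** Formal comparison of the arms is at month 3. Changes at six and nine months are descriptive, without hypothesis tests.

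**The concern.** The chain is a claim about order: confidence changes first, then self-management, then physical QOL. At month 3, the last visit before the waitlist arm starts the intervention, all three are observed at once. A participant who breathes better after exercise training may then rate both their mastery and their self-management higher, which is the chain run backwards. The framework section itself says that exercise acts on COPD physiology, so a route to better QOL that bypasses self-management is plausible on the plan's own terms.

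Randomisation protects the effect of the arm on each construct. It does not protect the links between constructs, because neither self-efficacy nor self-management is randomised. Mastery and physical QOL also share a questionnaire, so common-method correlation could look like support.

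At stake is the mechanistic conclusion. A good fit and significant forward paths could be reported as confirming the framework when the opposite order would have produced the same output.

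**Working it through.** The plan gives no figure for this analysis, so there is none to reproduce. The check asks whether the planned criteria can tell the stated order from its reverse.

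**Inputs from the documents (Sample Size; Analysis Plan).** 200 enrolled 1:1, with 5% attrition: 200 × 0.95 = 190. Two-sided 5% tests. CRQ difference 0.5 and SD 1.13: 0.5/1.13 = 0.44 SD, used as the arm effect on QOL.

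**Assumptions, because the documents give none.** Standardised paths between constructs of 0.3, 0.4 and 0.5. Direct arm effects on the two later constructs of 0, 0.15 and 0.30 SD. Models were fitted to observed scores as recursive regressions.

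**Step 1: equivalence when the arm may act on all three.** Write X for arm, SE for self-efficacy, SM for self-management and Q for physical QOL.

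- Forward: X→SE, X→SM, X→Q, SE→SM, SM→Q.
- Reversed: X→Q, X→SM, X→SE, Q→SM, SM→SE.

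Each has one testable restriction, and it is the same one: SE and Q are uncorrelated given SM and X. The two models therefore imply the same covariance matrix. Chi-square, GFI and RMSEA are computed from that matrix and must agree. In simulation the largest chi-square difference was about 5e-13, which is rounding error. With the same measurement model for the latent constructs, the argument carries over to the structural part of the SEM.

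**Step 2: truth reversed (X→Q→SM→SE), forward model fitted, arm acting on all three.**

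| Path | Direct arm effect | SE→SM and SM→Q both significant | Chi-square not rejected | Full X→SE→SM→Q path significant |
|---|---|---|---|---|
| 0.3 | 0 | 97.8% | 94.3% | 6.4% |
| 0.3 | 0.15 | 97.9% | 94.6% | 34.1% |
| 0.3 | 0.30 | 97.3% | 94.4% | 80.0% |
| 0.4 | 0 | 100% | 94.4% | 7.6% |
| 0.4 | 0.15 | 100% | 94.2% | 47.7% |
| 0.4 | 0.30 | 100% | 94.6% | 91.8% |
| 0.5 | 0 | 100% | 95.0% | 12.4% |
| 0.5 | 0.15 | 100% | 94.6% | 63.5% |
| 0.5 | 0.30 | 100% | 94.8% | 97.0% |

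A hand check uses the Fisher transform with one covariate, √(190 − 4) = 13.64. For a path of 0.3, atanh(0.3) = 0.3095 and 0.3095 × 13.64 = 4.22. Power is Φ(4.22 − 1.96) = 0.988 per path, and 0.988² = 0.976 for both. For a weaker path of 0.2, 0.2027 × 13.64 = 2.76, so power is 0.79 per path and 0.79² ≈ 0.62 for both. Over this wider range the rate runs from about 63% to 100%.

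**Step 3: strict chain, arm acting only on the first variable.** The two models are no longer equivalent. With the truth reversed, the forward chain was rejected by chi-square (3 df) in 71.1%, 69.2% and 70.4% of trials for paths of 0.3, 0.4 and 0.5. Its full path was significant in 5.5%, 8.5% and 11.8%. Other runs with assumed coefficients gave rejection rates of about 66-73%.

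**Step 4: baseline adjustment alone.** In a two-construct version (truth X→Q→SM only, reverse paths 0.2, 0.4, 0.6), the false X→SM→Q path was significant in 7%, 22% and 43% of trials, and in 8%, 29% and 57% with baseline adjustment. Other assumed values gave 11%, 24% and 45%, and 14%, 47% and 73%. Baseline correlation and month-to-month stability are not in the documents, so only the pattern matters: adjusting for baseline does not settle direction.

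**The case against.** The strongest reply is that the Path analysis paragraph describes a restricted chain. Its list of direct effects has MI training acting on self-efficacy only, with its effects on self-management and QOL named as mediated. For that model the randomised arm does give leverage, and Step 3 shows it. This stands. A reader might infer that reverse causation would always give the same result; the documents do not support that, because the strict chain is one fair reading of the text. It is not the only one, since the predictor-to-outcome sentence lets predictors act on all three constructs. The plan also neither states nor defends the assumption that rehabilitation reaches physical QOL only through self-efficacy and self-management. Even under the strict chain, roughly 3 in 10 simulated trials would not reject the wrong order.

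Second, the path analysis is not one of the three quantitative hypotheses, the analysis text says the framework is to be tested, and the word confirm appears only in the background. This also stands and limits the weight of the point. A reader might infer that the trial's evidence on behaviour change is compromised. It is not: Aim 2 has its own randomised comparison of SMAS-30 at month 3.

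Third, one might conclude that a lagged model should replace the concurrent one. That does not follow either. When self-management truly raised QOL but only during rehabilitation, a lagged model conditioning on end-of-rehabilitation QOL detected it in about 5% of simulated trials, which is no better than chance. Detection was 54-99% if the effect continued afterwards. The plan is silent on lags; it does not rule them out.

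**Conclusion.** The point holds in limited form. Same-visit measurement, a randomised package with non-randomised mediators, and reliance on global fit mean that the planned analysis cannot confirm the direction of the chain.

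- If the arm may act on all three constructs, the stated and reversed orders fit identically. This is exact and needs no assumed coefficient.
- In that model, significant forward links are the usual result even when the truth is reversed: 97-100% of trials for paths of 0.3-0.5, and about 63% at 0.2. Whether the full path from arm to QOL is also significant depends heavily on how far the arm shifts each construct directly (6-97%).
- If the arm acts on self-efficacy alone, the wrong order is rejected in roughly 65-75% of trials, so the data carry some information about direction.

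The percentages rest on N = 190, an arm effect of 0.44 SD, assumed path coefficients and observed rather than latent scores. They show the pattern and do not predict this trial's result. The consequence is confined to a secondary mechanistic claim; the month-3 comparisons for Aims 1-3 are untouched.

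**What to change.** **Path analysis paragraph.** State that the path model uses month-3 values adjusted for baseline values, and say which direct arm effects are included. Report it beside the reversed-order model (QOL to self-management to self-efficacy), with fit indices and path estimates for both. State that the links between constructs are read as association.

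**Theoretical Framework.** Replace the statement that the analysis will confirm the framework with one that it will examine whether the data are consistent with it.

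**Optional.** A lagged model may be added as an exploratory sensitivity analysis only: mediators at each arm's end of rehabilitation (month 3 intervention, month 6 control) and QOL three months later (months 6 and 9). It should carry four caveats:

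- It is not a randomised contrast.
- It loses participants who miss later visits.
- Measurement error can bias it. At an assumed reliability of 0.85, its false-positive rate was 5-12% under one set of assumptions and 7-22% under another.
- It has no power for mediation completed during rehabilitation.

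It should not replace the concurrent model, and an exploratory label keeps it in line with the plan's descriptive treatment of later data.

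**Cost.** A small amount of extra analysis on data already scheduled for collection, and a weaker mechanistic claim.
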